### 7.2. Safety Evaluations

The safety in this study will be monitored on a frequent and regular basis and will be formally reviewed on a monthly basis by the study investigators, who are experienced in the treatment of alopecia, the Sponsor's medical monitor, and the clinical director. In addition to reporting adverse events throughout the study, the investigator, a designated and appropriately trained staff member or the subject, will perform study specific safety assessments according to the schedules noted below.

An independent safety monitor will review the safety data monthly or more frequently, if needed.

#### 7.2.1. ECGs

At Visits 1, 2, 10 and 11 a standard 12-lead ECG will be performed by a qualified staff member. The ECGs must be obtained using a standard 12-lead ECG with a 10mm/mV amplitude, at 25mm/sec and a 5-10-second duration. To ensure a steady heart rate the subject must rest quietly in the supine position for at least 5 minutes prior to performing the ECG.

A central lab will provide equipment, supplies and site training. In addition, the central lab will process the ECGs received by the sites and report results via a secure study portal. The ECG results will be interpreted by a qualified health professional (evaluator) and the interpretation reported either directly on the tracing or in a separate report. The evaluator will interpret the results of every ECG and define the ECG as “normal” or “abnormal”. Variations such as minor ST changes (*i.e.*, <0.5mm depression) and early re-polarization are considered normal.

The investigator must review the evaluator’s interpretation of each subject’s Visit 1 ECG prior to Visit 2. The investigator will review the evaluator’s interpretation of all ECG reports in a timely manner and comment on the clinical significance of any result that is defined by the evaluator as abnormal.

Any abnormalities that are, in the opinion of the investigator, CS must be reported as medical history if found prior to the start of the first study medication application or as an AE if found after the start of the first study medication application.

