**Study Design:**

This is an open-label study which will be conducted at 1 to 2 sites.

Subjects will be required to have a clinical diagnosis of AA, AU or AT with unilateral or bilateral loss of eyebrow hair with a duration of the current episode of at least 6 months, but not more than seven years. A total of approximately 12 subjects will apply ATI-50002 Topical Solution 0.46%, to the affected eyebrow(s) twice-daily (BID) for 24 weeks.

After completing Visit 1 (start of the screening period), subjects will be assessed for eligibility to receive study medication.

Subjects will apply study medication to the entire affected eyebrow(s), twice-daily for 24 weeks. The 24-week treatment period will be followed by a 4-week no-treatment follow-up period. Assessment of response to treatment will be performed at Week 4, Week 8, Week 12, Week 16, Week 20, Week 24 and Week 28.

Safety and tolerability will be evaluated throughout the study by assessment of electrocardiograms (ECG), clinical laboratory tests, adverse events and vital signs.

The duration of the study participation is anticipated to be a maximum of 233 days (an up to 28-day screening period, a 169-day treatment period with a 4-day window, a 28-day no-treatment follow-up period with a window of 4 days).

Study visits are:

- Visit 1 (Day -28 to 0): screening; start eligibility assessment period
- Visit 2 (Week 0): initiation of twice-daily study medication application

CONFIDENTIAL

Page 7 of 57

- Visits 3-10 (Weeks 1-24): treatment period
- Visit 11 (Week 28): no-treatment period follow-up; end of study

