- QTcF  $>450\text{msec}$  for males or  $>470\text{msec}$  for females (use of the ECG algorithm is acceptable for this purpose)
- Heart rate  $<45$  or  $>100$  beats/minutes (inclusive)
- Rhythm disturbance other than sinus arrhythmia or ectopic supraventricular rhythm (ectopic atrial rhythm)
- Conduction disturbance including PR  $>240\text{msec}$ , pre-excitation (delta wave and PR  $<120\text{msec}$ ), second degree or higher AV block
- Acute or chronic signs of ischemia
- Left Bundle Branch Block
- Prior myocardial infarction

**Criteria for Evaluation:***Efficacy:*

The investigator will evaluate the severity of eyebrow loss using the Clinician's Eyebrow Assessment. Subjects will evaluate the severity of eyebrow loss using the Subject's Eyebrow Assessment.

*Safety:*

The investigator will assess clinical laboratory safety tests, vital sign readings, concomitant therapies, urine pregnancy test results, and adverse event (AE) information throughout the study.

*Other:*

Subjects will assess their satisfaction with the status of each eyebrow using the Subject Eyebrow Satisfaction scale. Standardized color photographs to assist with documenting the status of the subject's eyebrows will be taken throughout the study.

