### **8.2.3. Safety Monitoring ECG Discontinuation Criteria**

Any subject who develops any of the following ECG criteria during the active treatment phase will be instructed to stop study medication and will be withdrawn from the study:

- A post-study medication ECG result where the evaluator’s interpretation shows any of the following:
  - Clinically significant rhythm disturbance other than sinus rhythm or ectopic supraventricular rhythm (ectopic atrial rhythm)
  - Clinically significant conduction disturbance including PR >240msec, pre-excitation (delta wave and PR <120msec), second degree or higher AV block

CONFIDENTIAL  
Page 45 of 57

- New finding of QRS>120ms (if not present at screen. For example, subjects with Right Bundle Branch Block at screening would not need to be withdrawn from the study if their subsequent ECGs remained unchanged)
- Evidence of QT-interval prolongation, defined as an increase in the QTcF interval >60ms from Visit 1
- New QTcF > 500 ms
- Acute signs of ischemia or infarction
- Any ECG abnormality which may, in the opinion of the investigator, represent a new medical issue of concern

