## **10. STATISTICAL ANALYSES**

### **10.1. Statistical Methods**

Summary descriptive statistics (N, mean, median, SD) by visit will be provided for all safety and efficacy parameters. Primary and secondary efficacy parameters are described below:

Mean change from baseline in eyebrow growth will be calculated as the mean change in the Clinician's Eyebrow Assessment (CEA) from Visit 2 (Baseline) compared to end of treatment (Visit 10). The CEA evaluates eyebrows on a scale from "No eyebrow hair" (grade 0) to "Full eyebrow hair" (grade 4).

Mean change from baseline in the Subject's Eyebrow Assessment (SEA) will be calculated from Visit 2 (Baseline) to end of treatment (Visit 10).

Mean change from baseline in the Subject's Eyebrow Satisfaction (SES) will be calculated from Visit 2 (Baseline) to end of treatment (Visit 10).

All efficacy summaries will be based on the per-protocol population including all subjects who have Baseline (Visit 2) and Visit 10 efficacy data and no major protocol violations.

Safety analyses will include descriptive statistics calculated on the safety parameters using the safety population. The proportion of subjects with treatment-emergent adverse events will be tabulated and presented by Medical Dictionary for Regulatory Activities (MedDRA) System Organ Class. Vital signs and clinically significant abnormal laboratory results will also be

CONFIDENTIAL  
Page 49 of 57

tabulated and presented. Change from baseline in the Local Tolerability Assessments (LTA) to end of treatment (Visit 10) will be summarized.

Data from all enrolled and treated subjects will be presented and summarized. Safety summaries will include listings by study medication of adverse events incidences within each MedDRA System Organ Class, and changes from pre-application values in vital signs. Adverse event summaries will be presented by study medication showing the proportion of subjects experiencing adverse events, both overall and by MedDRA System Organ Class.

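### Does Section 10.1 need an ECG output tied to the Section 8.2.3 stopping criteria, given that Visit 10 is the only scheduled on-treatment post-dose ECG?

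*Combined protocol and SAP*

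**What the plan says.** Section 7.2.1 gives the timing: "At Visits 1, 2, 10 and 11 a standard 12-lead ECG will be performed by a qualified staff member". The visit lists in Sections 6.3.1 to 6.3.5 agree with it, and the list for Visits 3 to 9 contains no ECG. At Visit 2 the ECG is step 6, ahead of dispensing (step 7) and the observed first application (step 8). At Visit 10 all medication is collected.

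Section 8.2.3 attaches a consequence to ECG findings: "Any subject who develops any of the following ECG criteria during the active treatment phase will be instructed to stop study medication", with withdrawal from the study. It applies to any tracing taken after dosing has begun, scheduled or not. One criterion is "an increase in the QTcF interval >60ms from Visit 1".

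On reporting, the Synopsis (Study Design) says "Safety and tolerability will be evaluated throughout the study by assessment of electrocardiograms (ECG), clinical laboratory tests, adverse events and vital signs". The Synopsis list of safety criteria does not mention ECGs: "The investigator will assess clinical laboratory safety tests, vital sign readings, concomitant therapies, urine pregnancy test results", followed by adverse events. Section 10.1 opens with a general commitment: "Summary descriptive statistics (N, mean, median, SD) by visit will be provided for all safety and efficacy parameters". It then names outputs for adverse events, vital signs, clinically significant laboratory abnormalities and local tolerability (for example "Vital signs and clinically significant abnormal laboratory results will also be" tabulated). It does not name ECGs.

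Section 7.2.1 also routes findings by timing. "Any abnormalities that are, in the opinion of the investigator, CS must be reported as medical history" if seen before the first application, and as an adverse event if seen afterwards.

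**The concern.** The protocol has a withdrawal rule based on ECGs but no scheduled ECG that could trigger it until the visit at which treatment ends. Before then, only an unscheduled tracing could do so. If the report said that no subject stopped for an ECG reason, a reader might take this as none of about 12 subjects, although the number who had any ECG between Day 1 and Visit 10 might be zero.

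The second worry is a subject who meets a criterion and appears in no named output. A by-visit mean can hide one large value. The adverse event tables depend on the investigator's view of clinical significance, whereas the QTcF and QRS criteria in Section 8.2.3 carry no such condition. The reference points also differ: Section 8.2.3 measures the QTcF increase from Visit 1, while Section 10.1 uses Visit 2 as baseline for the efficacy scales. Safety is part of the main objective, and in a small uncontrolled study a single case matters.

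**Working it through.** **Schedule.** Inputs: ECG visits from Section 7.2.1, visit weeks and windows from Sections 6.3.2 to 6.3.5, about 12 subjects from Section 5.1. Study day = 7 × week + 1.

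| ECG visit | Week | Day | Status |
|---|---|---|---|
| 1 | screening | −28 to 0 | before dosing |
| 2 | 0 | 1 | before dosing, by list order |
| 10 | 24 | 7 × 24 + 1 = 169 | post-dose, end of treatment |
| 11 | 28 | 7 × 28 + 1 = 197 | off treatment |

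- Planned tracings: 4 × 12 = 48, of which 1 × 12 = 12 are post-dose within the treatment period, all at Visit 10.
- Gap from first application to Visit 10: 169 − 1 = 168 days; with the ±4-day window, 164 to 172.
- Planned subject-days in that gap: 12 × 168 = 2,016.

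The schedule is therefore as the concern describes it.

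**Can a by-visit summary hide one case?** Assume one subject at +61 ms and eleven at 0.

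- Mean = 61/12 = 5.08 ms; median = 0.
- SD = √[(61² − 61²/12)/11] = √(3,410.9/11) = 17.61 ms.

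The mean and median do not identify the case. Setting eleven subjects at exactly zero is artificial, and Section 10.1 does not itself specify an ECG change score.

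**Does the choice of reference matter?** Assume QTcF of 400 ms at Visit 1, 410 at Visit 2 and 465 at Visit 10. From Visit 1 the change is 465 − 400 = 65, which meets the criterion. From Visit 2 it is 465 − 410 = 55, which does not. Section 10.1 plans no ECG change from Visit 2, however, so no stated rule yields the second figure. A safety threshold anchored at screening can stand beside an efficacy baseline at Visit 2.

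**Where would each kind of ECG information surface?**

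- *Which visits have ECGs.* ECG is a safety parameter (Section 7.2, Synopsis), so the general sentence in Section 10.1 covers it. The N by visit would show post-dose values only at Visits 10 and 11.
- *A clinically significant finding after dosing begins.* It becomes an adverse event under Section 7.2.1 and enters the adverse event tables.
- *A criterion met on treatment but judged not clinically significant.* Section 8.2.3 still requires withdrawal where the criterion has no significance condition. Section 5.6 requires the date and reason on the case report form and notice to the sponsor's study monitor within 24 hours.
- *A subject who leaves early for another reason.* Section 5.6 calls for an attempt at the final-day assessments, which include an ECG (Section 6.3.5). Such a tracing may fall before Visit 10, but it follows the decision to withdraw and cannot prompt it.
- *The tracings themselves.* Scheduled ECGs are processed by a central laboratory (Section 7.2.1), and Section 10.1 undertakes to present data from all enrolled and treated subjects.

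**The case for a change.** The best argument for a change is that none of these routes is a count. The general sentence gives N, mean, median and SD, and has no stated place for unscheduled tracings, the only kind that could cause an early stop. Section 10.1 specifies no table of withdrawals by reason. An assumed rise in QTcF from 380 to 442 ms is +62 and meets the criterion, yet lies below both screening limits of 450 and 470 ms, so it could be read as normal and never become an adverse event. One table and one listing would settle the matter with no extra ECG.

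Much of this is true: Section 10.1 specifies no categorical ECG output and no denominator for statements about ECGs before Visit 10. But the data are recorded, and no passage plans a statement that none of 12 subjects stopped for ECG reasons. The omission is not peculiar to ECGs, since Section 10.1 gives no count against the laboratory criteria in Section 8.2.4 either. Nor is the ECG omission in the Synopsis safety criteria telling: that list also leaves out local tolerability, which Section 10.1 does summarise.

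A count would also need care. Some criteria in Section 8.2.3 require clinical significance or rest on investigator opinion, so counting all of them regardless would not be the rule as written. Visit 11 lies outside the active treatment phase, and early-withdrawal tracings belong in a separate class. Those choices are ordinarily made in table shells.

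**Conclusion.** No change to the plan is needed. The schedule reading is right: one scheduled on-treatment post-dose ECG per subject, about 12 in all, none in the 168 days before Visit 10. The consequence feared does not follow in full, because N by visit, the adverse event tables and the recorded withdrawal reason together show most of what is said to be hidden. The remainder is a count of subjects meeting each Section 8.2.3 criterion, which no section specifies. It is a gap in detail: no stated rule produces a wrong result, and analysts of a descriptive study of about 12 subjects with no power calculation would be expected to list ECG results and any ECG-driven withdrawals.

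Sections 7.2.1 and 8.2.3 do not contradict each other, since the stopping rule applies to unscheduled tracings too. Nothing is said here about whether the schedule or the criteria are clinically suitable.

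The conclusion rests on three things. The pre-dose timing of the Visit 2 ECG is inferred from list order; if it were taken after application, it would be a Day 1 tracing and the later gap would stand. The ECG row of the flow chart in Section 6.2 was not legible in the available text, so the schedule was checked against Sections 6.3 and 7.2.1 only. And the general sentence in Section 10.1 is taken to include ECGs, as its wording implies.

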### **7.2.2. Brief physical examination**

At Visits 1 and 11 the investigator or designee will perform a brief physical examination. The examination will include an assessment of the following:

- General appearance
- Vital signs (Section 7.2.3)
- Head, eye, ear, nose and throat (HEENT)
- Respiratory
- Cardiovascular
- Abdominal
- Extremities
- Musculoskeletal
- Lymphatic
- Skin
- Neurological

Any measure that is, in the opinion of the investigator, abnormal AND CS must be recorded as medical history if found prior to the first study medication application or as an AE if found after the first study medication application begins.

### **7.2.3. Vital signs**

At Visits 1-11 a qualified staff member will measure vital signs. The following items will be measured:

- Body temperature
- Pulse rate
- Respiration rate

CONFIDENTIAL  
Page 37 of 57

- Blood pressure (systolic and diastolic) after the subject sits quietly for at least 5 minutes
- Height (at Visit 1 only)
- Weight (at Visit 1 only)

Any measure that is, in the opinion of the investigator, abnormal AND CS must be recorded as medical history if found prior to the first study medication application or as an AE if found after the first study medication application begins.

A systolic blood pressure >140mm Hg or a diastolic blood pressure >90mm Hg is considered abnormal and therefore must be defined as CS or not clinically significant (NCS) on the eCRFs. A weight >300 lbs. is considered abnormal and therefore must be defined as CS or NCS on the eCRFs.

#### 7.2.4. Clinical laboratory sampling

Subjects will go to a local laboratory (to be determined) to have the clinical laboratory tests at Visits 1, 2, 7, 10 and 11. WOCBP will have urine pregnancy tests performed by the study staff at Visit 2, 5, 6, 7, 8, 9, 10 and 11. Approximately 22.5ml of blood will be collected at Visit 1 and 10.5ml for each sample at Visits 2, 7, 10 and 11, a total of approximately 64.5ml per subject for the entire study. The following tests, at a minimum, will be conducted:

Chemistry Panel	Complete Blood Count
Albumin	Hematocrit
Alkaline phosphatase	Hemoglobin
Alanine aminotransferase (ALT)	Platelet count
Aspartate aminotransferase (AST)	Red blood cell morphology
Blood urea nitrogen (BUN)	Red blood cell count
Bicarbonate	White blood cell count
Calcium	White blood cell differential
Chloride	% & absolute
Creatinine	Basophils
Glucose	Eosinophils
Lactate dehydrogenase (LDH)	Lymphocytes
Phosphorus	Monocytes
Potassium	Neutrophils
Sodium	
Total bilirubin	Complete Urinalysis
Total protein	
Uric acid	
Total cholesterol, LDL, HDL	
Triglycerides	

#### Screening Tests Only

Virology (HepB, HCV, HIV)  
 Total Iron Binding Capacity (TIBC)  
 Serum Iron

Serum Ferritin  
T3/T4, TSH  
Quantiferon  
Serum Pregnancy (Visit 1 only)

The results of the clinical laboratory tests will be reported on the laboratory's standard reports. The investigator must review all laboratory reports in a timely manner and note NCS or CS to define the clinical significance of any result that is outside the normal range for the laboratory. The investigator must date and initial every laboratory report.

The investigator must review the Visit 1 laboratory results for all the required analytes for each subject prior to Visit 2. The subject must not continue in the study and apply study medication if at Visit 2 any of the Visit 1 results are outside normal range for the laboratory AND, in the opinion of the investigator, CS.

The investigator must report all laboratory results that are BOTH outside the normal range for the laboratory AND, in the opinion of the investigator, CS as medical history if found prior to the first study medication application or as an AE if found after the first study medication application begins.

### **7.2.5. Local Tolerability Assessment (LTA)**

The LTA is the investigator's assessment of the average overall severity of signs and the subject's assessment of the average overall severity of symptoms associated with irritation on each eyebrow considered separately. The investigator and subject must NOT refer to any other evaluation to assist with these assessments. This is not a comparison with the assessment at any other time point.

At Visits 2-11, the investigator and the subject will evaluate the LTA signs and the LTA symptoms respectively.

LTA Signs (assessed by the investigator for each eyebrow separately):

- Erythema
- Edema
- Scaling/dryness

LTA symptoms (assessed by the subject for each eyebrow separately):

- Stinging
- Burning

The investigator will assess the LTA signs as follows:

- At Visit 2:
  - Prior to the first study medication application
  - 20 ( $\pm 4$ ) minutes after the application completion time.
- At Visits 3-11

CONFIDENTIAL  
Page 39 of 57

The subject will assess the LTA symptoms as follows:

- At Visit 2:
  - Prior to the first study medication application report the LTA for each symptom over the previous 24 hours
  - 10 ( $\pm 4$ ) minutes after the application completion time report the average severity since the application completion time
- At Visits 3-11:
  - Report the average LTA for each symptom over the previous 24 hours

The investigator, for the signs, should report the one integer that best describes the average overall severity on each eyebrow separately using the scales below:

**Local Tolerability Assessment – Erythema**

Grade	Descriptor
0	Clear: No erythema present
1	Mild: Slight erythema
2	Moderate: Definite erythema
3	Severe: Marked, fiery erythema

**Local Tolerability Assessment – Edema**

Grade	Descriptor
0	Clear: No edema present
1	Mild: Slight edema
2	Moderate: Definite edema
3	Severe: Marked edema

**Local Tolerability Assessment – Dryness/Scaling**

Grade	Descriptor
0	Clear: No signs of dryness or scaling
1	Mild: Slight roughness (may be more easily felt than seen), barely perceptible scaling
2	Moderate: Moderate roughness, definite scaling
3	Severe: Marked roughness, heavy scaling

The subject, for the symptoms, should report the one integer that best describes the average overall severity on each eyebrow separately using the scales below:

**Local Tolerability Assessment – Stinging**

Grade	Descriptor
0	Clear: No stinging
1	Mild: Slight tingling, not bothersome
2	Moderate: Definite tingling, slightly bothersome
3	Severe: Intense stinging, bothersome and/or uncomfortable

### **Local Tolerability Assessment – Burning**

Grade	Descriptor
0	Clear: No burning
1	Mild: Slight warmth, not bothersome
2	Moderate: Definite warmth, slightly bothersome
3	Severe: Intense feeling of heat, bothersome and/or uncomfortable

Follow these steps to complete the LTA for each symptom by a subject:

- An investigational center staff member, other than the evaluating investigator, will show the appropriate LTA symptom grading scale to the subject and instruct the subject on the time interval to be considered.
- The staff member should not give any opinion on the meaning of the LTA descriptors.
- The subject should verbally indicate the appropriate grade for each eyebrow for each symptom and the staff member will report the grade in the source document.
- Both the subject and the staff member must sign/initial the source document to indicate the subject performed the LTA for symptoms as instructed.
- The staff member must not influence the subject's assessment.

